**Versjon 1.2**

## **1. Background and rationale**

Transcatheter Aortic Valve Implantation (TAVI) has become a preferred treatment for patients with severe aortic stenosis who are at high or intermediate surgical risk (1). However, when compared to surgical aortic valve replacement, TAVI less often results in commissural alignment (2). Optimizing commissural alignment between the transcatheter valve and the native aortic valve is critical in preserving future coronary access, especially for younger patients and patients with known coronary artery disease that may require percutaneous coronary intervention (PCI) after TAVI (3, 4). In addition, an increasing number of patients are considered for redo-TAVI if failure of their first TAVI-valve occurs. Commissural misalignment impacts the feasibility of a redo-TAVI procedure, because of risk of sinus sequestration and coronary obstruction as well as the possibility for leaflet modification techniques of their prior TAVI valve (3). It may also have effects on valve functionality and durability (5, 6). Current implantation techniques vary in their ability to obtain commissural alignment, which impact coronary artery access and PCI after TAVI as well as redo-TAVI procedures (7, 8).

The latest-generation self-expandable Evolut FX+ TAVI valve offers potential benefits in achieving commissural alignment or later better coronary access compared to older generations of the Evolut family (3, 4). Khera et al. compared Evolut FX and Evolut PRO+ in a non-randomized trial. They concluded that the new design features of the Evolut FX system appeared to significantly improve the ability to achieve commissural alignment (4). Later, the FX+ valve has been released, which incorporates a modified frame with larger coronary

access windows to improve catheter maneuverability and access to coronary arteries. Recent work has indicated that the position of the delivery system in the descending aorta is important for commissural alignment and avoidance of coronary overlap (7). Furthermore, Konami et al recently demonstrated that rotation of the fluoroscopic "Hat" marker in the descending aorta is useful for improving commissural alignment in TAVI with Evolut devices (8). Currently, it is common that the operator rotates the delivery system in a left anterior oblique (LAO) projection to achieve that the "Hat" marker is facing the great curvature of the descending aorta before crossing the aortic arch, but at which LAO degree this should be performed has not been established.

On this background, we believe that the optimal implantation technique to obtain the best possible commissural alignment and subsequent coronary access with the Evolut FX+ for each specific patient remains unclear and warrants further investigation. This is underpinned by recent data supporting that patient-specific rotation with the self-expanding "ACURATE neo" TAVI-valve, based on computed tomography (CT)-analysis obtained before implantation, may improve the success rate of commissural alignment (9). Also, another study by Bieliauskas et al. based a patient- and valve-specific implantation technique on each patient's pre-operative CT (three types of valves; Evolut R/PRO, ACURATE neo2, Portico), which allowed for safe and reproducible implantation (10). The purpose of the present study is to prospectively evaluate the efficacy and safety of a novel patient-specific rotation of the Evolut FX+ TAVI valve and the delivering system during the transfemoral (TF) procedure. Specifically, it aims to evaluate and compare the commonly used fluoroscopic (X-ray) LAO degree for rotation of the delivery system and more patient-specific LAO degree achieved by CT analysis prior to the procedure. The degree of alignment and coronary overlap will be measured with ECG-gated CT after the procedure. Thus, it will prospectively explore if these two techniques differ in obtaining commissural alignment, coronary overlap and safety outcomes following implantation of latest-generation Evolut FX+ valve.

## **2. Study objectives**

In patients with severe aortic stenosis indicated for TF-TAVI with the Evolut FX+ valve after multidisciplinary heart team meeting:

### **Primary Objective:**

- To investigate and compare commissural alignment of two rotational positioning methods based on the positioning of the fluoroscopic "Hat" marker at the descending aorta with the Evolut FX+ valve.

### **Secondary Objective:**

- To evaluate and compare the likelihood of successful post-TAVI coronary access assessed by CT after TAVI with the Evolut FX+ valve.

[figure not shown]
### 3. Study hypotheses

In patients with severe aortic stenosis indicated for TF-TAVI with the Evolut FX+ valve after heart team meeting:

1. A strategy of patient-specific rotation will be superior to a generalized approach in obtaining commissural alignment.
2. A strategy of patient-specific rotation will increase the likelihood of successful post-TAVI coronary access assessed by CT after TAVI with the Evolut FX+ valve.

### 4. Overview of study design

- Randomized, prospective, single-center observational study.

## **5. Study sample**

5.1. Target enrollment: 40 patients.

5.2 Inclusion criteria:

- Patients with severe aortic stenosis indicated for TAVI after heart team meeting.
- Age  $\geq 65$  years.
- Patients planned by the TAVI team to receive a self-expandable valve (Evolut FX+ valve).
- Patients providing informed consent.

5.3 Exclusion criteria:

- Severe peripheral vascular disease preventing transfemoral access.
- Prior aortic valve replacement or bicuspid valve.
- Severely reduced kidney function (estimated glomerular filtration rate  $< 30$ ).

## **6. Randomized treatments**

Subjects will be randomized to a patient-specific rotational method or a conventional generalized rotational method before the procedure.

## **7. Study procedures**

7.1 Overview of study procedures

### **Pre-procedural (standard) assessment**

- Baseline CT scan to evaluate aortic root anatomy by using 3mensio analysis software.
- Clinical and echocardiographic assessment (left ventricular function, aortic valve area, mean gradient).
- Coronary angiography to assess native coronary anatomy.
- Blood tests.

### **Procedural steps**

- Valve implantation: The Evolut FX+ valve will be implanted using standard transfemoral access under fluoroscopic guidance.
- Rotational positioning methods:
  - **Method 1** (generalized approach): The “Hat” marker positioned in the descending aorta with fluoroscopy at 25 degrees left anterior oblique.
  - **Method 2** (patient-specific approach): The “Hat” marker positioned in the descending aorta with fluoroscopy at the pre-procedural identified degree at which the right and non-coronary cusp overlap (from CT analysis).

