## 7.2. Screening and recruitment

All patients with severe aortic stenosis indicated for TAVI with the Evolut FX+ valve after heart team meeting at Oslo University Hospital (OUS) Ullevål will be screened for eligibility and screening logs will be registered during the whole study period. Potential participants will be identified after the heart and TAVI meetings have been completed, as only those who receive a decision for Evolut FX+ will be asked to participate in the study (there are always two operators from the intervention group present and all operators at the section (5 operators) will be involved in the recruitment by notifying the study group if patients have been approved for TAVI with Evolut FX+. The participants will then receive written and verbal information from one of the individuals in the study group or one of the treating physicians at the department (either in-hospital during their pre-operative evaluation so that they will have time to evaluate over days/weeks before they possibly consent to inclusion, or alternatively early during admission for surgery so that patients will have sufficient time to evaluate if they want to participate (at least the day before)). All participants will meet and receive information from a study group member ([name], [name], [name], [name], [name]) before giving consent, and this study group member will not be in a "treatment relationship" with the patient (ref. 7.3 and paragraph 13 of the Health Research Act) .

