## 7.4. Randomization

Randomization will be performed using sealed envelopes, each containing a pre-determined treatment assignment, that are opened sequentially as participants are enrolled. This process helps to maintain allocation concealment and reducing the potential for selection bias.

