## 7.6 Variable list

A detailed variable list is attached as supplementary information to the present protocol.

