## 8. Study outcomes

### 8.1 Primary efficacy outcomes

- Proportion of patients achieving commissural alignment post-TAVI (measured by CT-analysis after TAVI).
- The relationship between alignment and rotational positioning method after TAVI.

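### Does the plan need the CT cusp-overlap angle in Method 1 patients to answer its question?

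*Protocol*

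**What the plan says.** Protocol section 7.1 (Procedural steps) defines the two arms by the projection in which the marker is positioned. Method 1 has the "marker positioned in the descending aorta with fluoroscopy at 25 degrees left anterior oblique". Method 2 uses "fluoroscopy at the pre-procedural identified degree at which the right and non-coronary cusp overlap (from CT analysis". The same section lists, as standard pre-procedural assessment without limit to one arm, "Baseline CT scan to evaluate aortic root anatomy by using 3mensio analysis software", and the table of study procedures marks CT at baseline.

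On what is recorded, section 7.6 says "A detailed variable list is attached as supplementary information to the present protocol". That list is not among the material at hand.

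Sections 2 and 3 frame the question as a comparison of two positioning methods. Section 8.1 names the proportion aligned and "The relationship between alignment and rotational positioning method after TAVI" as primary outcomes. Section 11 compares the proportion aligned (0 to 15 degrees), reports that no power calculation was done, and describes the group comparisons as descriptive and mainly hypothesis-generating.

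**The concern.** Where a patient's CT cusp-overlap angle happens to be 25 degrees LAO, the two methods are the same manoeuvre. The contrast between arms therefore depends on how far patients lie from 25. Section 1 gives as background that "at which LAO degree this should be performed has not been established", and section 13 wants the pilot to show whether a difference exists, how large it is, and whether a larger study is appropriate.

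The direct check on whether the angle matters would be to see if Method 1 patients far from 25 are the misaligned ones. That needs the angle in Method 1. Section 7.1 mentions it only under Method 2, and no comparison in sections 8.1 or 11 uses it. If the angle were truly unavailable in Method 1, a small arm difference could be misread as showing that the angle is unimportant, when the patients simply lay near 25.

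**Working it through.** There is no stated power or effect size to reproduce. The point turns on the text; the arithmetic only shows scale.

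**1. Is the angle confined to Method 2?** The wording under Method 2 fixes the projection used in that arm. It does not say that the angle is read in that arm alone. Every patient has the baseline CT with root analysis. That scan precedes the implant, so a reader unaware of the outcome could take the angle from it at any later date; section 14 keeps the data in research use until May 2031. The variable list may already contain the angle.

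**2. Do the stated aims need it?** Sections 2, 3, 8.1 and 11 all compare methods. Randomisation makes the difference in proportions aligned a valid estimate of the effect of the strategy, whatever the distribution of angles. No stated aim requires a relation between angle and misalignment within Method 1.

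**3. Would a null result be uninterpretable?** No. By randomisation the Method 2 patients are a sample of the same population. Assume 20 per arm (target enrolment is 40; the ratio is not stated) and an angle SD of 10 or 15 degrees. The standard error of the mean distance from 25 is:

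- Method 2 only: 10/√20 = 2.2; 15/√20 = 3.4 degrees
- All 40 patients: 10/√40 = 1.6; 15/√40 = 2.4 degrees

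Mean distances of 0 and -15 degrees lie 15/2.24 = 6.7 or 15/3.35 = 4.5 standard errors apart on Method 2 alone. That is enough to tell whether the population is centred near 25, and the spread of angles is seen there too.

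**4. What would the extra analysis add?** Assume a residual SD of 10 degrees and Method 1 misalignment that changes by k degrees per degree of distance. Method 1 then follows N(k(μ-25), (k·SD)² + 10²), Method 2 follows N(0, 10²), and a patient is aligned if within 15 degrees.

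For k = 1 and angles centred on 25 (μ = 25):

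- Method 2 aligned: 2Φ(15/10) - 1 = 0.866
- Method 1 aligned, SD 10: 2Φ(15/√200) - 1 = 0.711, a difference of 15.5 points (95% half-width 24.8)
- Method 1 aligned, SD 15: 2Φ(15/√325) - 1 = 0.595, a difference of 27.2 points (half-width 26.2)

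Simulated frequency of p < 0.05 (4,000 trials per scenario; SD 10 / SD 15):

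| Scenario | Planned test | t-test on degrees | Slope in Method 1 | Arm-by-distance interaction |
|---|---|---|---|---|
| k = 1, centre 25 | 14% / 40% | 26% / 62% | 53% / 87% | 37% / 76% |
| k = 1, centre 10 | 67% / 75% | 88% / 93% | 90% / 98% | 80% / 95% |
| k = 0.5, centre 25 | 3% / 6% | 7% / 13% | 13% / 30% | 8% / 20% |
| k = 0.5, centre 10 | 11% / 17% | 22% / 32% | 30% / 52% | 21% / 37% |

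At k = 1 the median 95% half-width of the interaction slope is 0.77 / 0.54 (centre 25) and 0.56 / 0.42 (centre 10). The mean fitted Method 1 slope is 0.62 to 0.85 instead of 1, because absolute values are used on both axes. The data are generated as linear in distance, which favours the regressions.

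A simpler gauge uses Fisher's z. The correlation in Method 1 detectable with 80% power at two-sided 0.05 is tanh((1.960 + 0.842)/√(n-3)): 0.67 at n = 15, 0.59 at n = 20, 0.54 at n = 25. At n = 20, an observed 0.5 has a 95% interval of about 0.07 to 0.77.

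**The case for a change.** The best case for raising the point is that the regression could wait for an SAP, but who reads the angle, in whom, when, and whether the operator sees it are study procedures that belong in section 7.1. Reading it from an existing scan is cheap. Where angles cluster near 25, the planned test would usually miss an effect that the Method 1 slope would more often pick up (14% against 53% in the first scenario).

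Part of this stands. The protocol text does not commit to recording the angle in Method 1, and doing so would be reasonable.

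The rest does not make it an error. The 53% and 87% belong to a slope within one arm. That is not a randomised contrast, since distance from 25 may track other anatomy, and it answers a different question from the planned test. The interaction, which guards against this, reaches only 8% to 37% at k = 0.5, and its interval is too wide to separate a full from a half effect. All these percentages rest on an assumed angle distribution, slope, residual SD and allocation ratio, and section 11 claims no confirmatory power.

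Reading every angle before allocation also has a price. A known angle could steer Method 1 cases unless it is kept from the operators, and the baseline CT is part of their standard work-up. The study members outside the treatment relationship are described in section 7.2 for information and consent, not for reading scans.

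**Conclusion.** The concern does not hold. The protocol states nothing wrong here, contradicts nothing, and fixes nothing that would block the analysis. The scans exist for all patients, and the randomised comparison of proportions matches the stated aims. The Method 2 angles place the population relative to 25 degrees to within a standard error of 2.2 to 3.4 degrees, given 20 per arm and an SD of 10 to 15. What is left is a preference for one more exploratory regression. It would gain most where angles lie near 25 and the effect per degree is large, and it would be imprecise even there. An analysis of that kind is commonly left to the SAP. The conclusion rests on the text and not on the simulated figures. If the unseen variable list omits the angle, it can still be read from the stored baseline scans.

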### **Post-procedural assessment**

- CT imaging:
  - Assessment of commissural alignment post-TAVI.
  - Coronary ostial relationship with the implanted valve.
- Clinical and echocardiographic assessment (left ventricular function, aortic valve area, mean gradient).
- Blood tests.
- Hospital chart review for safety endpoints.

Table of study procedures		TAVI-operation
	Baseline	Follow-up
Eligibility assessment	X	
Informed consent	X	
Randomization	X	
Patient demographics	X	
Clinical assessment and medications	X	
Medical history	X	
Blood tests	X	
ECG	X	
Echocardiography	X	
CT	X	
Complications		

## 7.2. Screening and recruitment

All patients with severe aortic stenosis indicated for TAVI with the Evolut FX+ valve after heart team meeting at Oslo University Hospital (OUS) Ullevål will be screened for eligibility and screening logs will be registered during the whole study period. Potential participants will be identified after the heart and TAVI meetings have been completed, as only those who receive a decision for Evolut FX+ will be asked to participate in the study (there are always two operators from the intervention group present and all operators at the section (5 operators) will be involved in the recruitment by notifying the study group if patients have been approved for TAVI with Evolut FX+. The participants will then receive written and verbal information from one of the individuals in the study group or one of the treating physicians at the department (either in-hospital during their pre-operative evaluation so that they will have time to evaluate over days/weeks before they possibly consent to inclusion, or alternatively early during admission for surgery so that patients will have sufficient time to evaluate if they want to participate (at least the day before)). All participants will meet and receive information from a study group member ([name], [name], [name], [name], [name]) before giving consent, and this study group member will not be in a "treatment relationship" with the patient (ref. 7.3 and paragraph 13 of the Health Research Act) .

## 7.3. Informed consent

Written informed consent after oral information and reading relevant documents will be obtained before the procedure. A copy of the signed consent document will be given to the patient and the original will be retained by the study personnel. The informed consent will be obtained in accordance with paragraph 13 of the Health Research Act. This means that the informed consent and signature will be obtained by a "neutral" person that is not involved in the treatment of the patient.

## 7.4. Randomization

Randomization will be performed using sealed envelopes, each containing a pre-determined treatment assignment, that are opened sequentially as participants are enrolled. This process helps to maintain allocation concealment and reducing the potential for selection bias.

## 7.5. Follow-up

Following the operation routine clinical follow-up will be performed as part of the standard procedure for all patients that are operated in our hospital. Standard clinical assessment, blood tests and safety endpoints will be reviewed and registered from the hospital chart. An ECG-gated CT scan of the heart after the TF-TAVI procedure will be performed during or a few days after the hospital stay.

## 7.6 Variable list

A detailed variable list is attached as supplementary information to the present protocol.

## 8. Study outcomes

### 8.1 Primary efficacy outcomes

- Proportion of patients achieving commissural alignment post-TAVI (measured by CT-analysis after TAVI).
- The relationship between alignment and rotational positioning method after TAVI.

### 8.2 Secondary efficacy outcome

- The likelihood of successful coronary access assessed by CT after TAVI.

### 8.3 Safety outcomes

- Pacemaker, vascular complications, pericardial effusion, open surgery, valve embolization, stroke, peri-procedural MI, kidney failure and death.

## 9. Data management

- All data will be de-identified and registered in “Medinsight”. Data will be obtained from hospital records reporting investigations that are performed in their usual clinical pathway. The only additional investigation that will be performed will be an additional CT-scan after the TAVI.

## 10. Withdrawal of participants

Participants may withdraw consent to participate at any stage of the study and for any reason.

## 11. Statistical considerations

- Commissural alignment will be reported and statistically compared by use of the proportion of patients achieving alignment (defined as 0 degrees to 15 degrees being commissural alignment, 15.1 degrees to 30.0 degrees being mild commissural misalignment, 30.1 degrees to 45.0 degrees being moderate commissural misalignment and 45.1 to 60.0 degrees being severe commissural misalignment) (3).

- Coronary access feasibility will be reported and statistically compared by use of proportion of patients achieving coronary access feasibility (defined as severe coronary overlap (within 0 degrees to 15 degrees) and less severe coronary overlap (>15 degrees)) (4).
- Safety outcomes will be reported and statistically compared by use of the proportion of patients with occurrence of each safety outcome.
- Categorical variables will be presented as numbers and/or percentages, and continuous variables will be presented as means (standard deviation) or medians (quartiles 1 to 3). Continuous variables will be compared with the t-test (if normally distributed) or the Mann-Whitney U test (if skewed). Categorical variables will be compared by using the Pearson chi square test or Fischer's exact test (if any field included <6). A p-value of < 0.05 will be regarded statistically significant, and all hypothesis testing will be two tailed.
- The potential difference in proportion of commissural alignment between the two techniques is unknown and thus no power calculation has been done. Comparisons between groups will therefore be descriptive and mainly hypothesis-generating.

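### Does section 11 leave open which coronary overlap band counts as feasible access?

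*Protocol*

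**What the plan says.** The only secondary efficacy outcome (section 8.2) is "The likelihood of successful coronary access assessed by CT after TAVI". The matching hypothesis in section 3 is "A strategy of patient-specific rotation will increase the likelihood of successful post-TAVI coronary access assessed by CT". Neither place gives a threshold. The list of post-procedural assessments in section 7.1 adds only "Coronary ostial relationship with the implanted valve".

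The threshold appears in section 11, which compares the "proportion of patients achieving coronary access feasibility (defined as severe coronary overlap (within 0 degrees to 15 degrees) and less severe coronary overlap", the second band being "less severe coronary overlap (>15 degrees"). The bullet just above it, on alignment, uses the same form but names its success band: "defined as 0 degrees to 15 degrees being commissural alignment".

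Section 11 also sets two-sided tests at 0.05, with Pearson's chi-square or Fisher's exact test for categorical variables. It says that no power calculation was done and that group comparisons are descriptive and mainly hypothesis-generating. Section 7.6 states: "A detailed variable list is attached as supplementary information to the present protocol". That list is not among the material at hand.

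**The concern.** A responder definition should say who is a responder. This one names both classes and stops. The unfavourable class comes first, inside the definition of a favourable outcome. The neighbouring bullet gives no safe pattern to copy: for alignment the 0 to 15 degree band is success, whereas for coronary overlap the same numerical band is the bad one. A reader who carried the pattern over would report the result the wrong way round.

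A second point goes with it. The outcome is a proportion of patients, but overlap can be measured at both the left and the right ostium, and section 11 does not say how the two give one patient-level answer. If nothing fixed that rule before the scans were read, the reported rate could depend on the choice.

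At stake would be the interpretation of hypothesis 2 and of the only secondary efficacy outcome.

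**Working it through.** The protocol gives no figure for this outcome, so there is none to reproduce. The check has three parts.

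**1. Can the wording be read in more than one sensible way?**

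| Reading of the parenthesis | Patients counted as feasible | Usable? |
|---|---|---|
| Either band (union) | all with a post-TAVI CT, 100% in each arm | no |
| Both bands at once, for a single angle (intersection) | none, 0% | no |
| A classification, success = 0 to 15 degrees | those with severe overlap | contradicts the outcome's name |
| A classification, success = above 15 degrees | those without severe overlap | yes |

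The first two readings give no comparison at all. The alignment bullet shows that the author uses this form to list a grading scheme, because it too runs through every band, from 0 to 60 degrees, after the words that introduce the definition. So the parenthesis is a classification. Between the last two rows, three pieces of text agree:

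- the 0 to 15 degree band is called severe;
- section 1 describes delivery-system position as "important for commissural alignment and avoidance of coronary overlap", so overlap is to be avoided;
- hypothesis 2 expects access to increase under the patient-specific method.

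Only the last row fits all three. The bands meet at 15 degrees without gap or double counting, so every measured angle falls in exactly one class.

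**2. What would depend on the label?**

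Let the two arms have a and c patients above 15 degrees, b and d patients at 0 to 15 degrees, and N patients in all.

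- Difference in proportions: with p1 = a/(a+b) and p2 = c/(c+d), calling the other band success gives (1 − p1) − (1 − p2) = −(p1 − p2). The size is the same and the sign is reversed.
- Pearson chi-square: N(ad − bc)² / [(a+b)(c+d)(a+c)(b+d)]. Swapping the columns turns ad − bc into bc − ad. Its square and the product of the margins are unchanged, so the p-value is the same.
- Fisher's exact test: swapping the columns maps each possible table to its mirror image with the same hypergeometric probability, so the two-sided p-value is the same.
- Choice between the two tests: section 11 bases it on whether any cell is below 6. The same four counts are present either way, so the choice is the same.

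Only the sign and the row heading in the results table depend on the label, and part 1 settles those. A risk ratio would change with the label, but section 11 plans a comparison of proportions and no ratio.

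**3. How much could the ostium rule matter?**

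All inputs here are assumptions; the protocol gives none. Let q be the probability of severe overlap at each ostium, taken as equal for left and right, and p11 the probability that both are severe.

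- Both ostia clear: 1 − 2q + p11
- At least one clear: 1 − p11
- Gap between the two rules: 2(q − p11)

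For q up to 50%, p11 can lie anywhere from 0 (never both in one patient) to q (always both). The gap therefore runs from 0 to 2q:

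| Assumed q | Full concordance, p11 = q | Independence, p11 = q² | Never both, p11 = 0 |
|---|---|---|---|
| 10% | 0 | 2(0.10 − 0.01) = 18 points | 20 points |
| 20% | 0 | 2(0.20 − 0.04) = 32 points | 40 points |
| 25% | 0 | 2(0.25 − 0.0625) = 37.5 points | 50 points |

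Independence is not the upper limit. One rotation of the prosthesis fixes both angles, which may make the ostia agree or may make overlap at one rule out overlap at the other. The documents do not say which. The table shows that a rule is needed somewhere. It does not show that one is missing, because the analysis plan and the variable list are not at hand.

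**The case for a change.** The best argument for a change is that the protocol is not merely silent here: it offers a definition, and that definition does not define success. An analysis plan can add detail but does not correct the protocol's wording. Section 13 says that coronary access will not be tested by selective angiography, so the CT rule is the only basis for any statement on access, and that the findings will help to judge whether a larger study is worthwhile. Even a descriptive proportion needs a numerator, and one sentence would supply it at no cost in data, scans or patients.

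Much of this is true. The parenthesis is badly phrased, no other section states the label, and a clearer sentence would do no harm. What does not stand is the step from poor phrasing to an open endpoint. The numerator can be recovered without guesswork, because the other candidate would count severe overlap as achieved access. The rewritten sentence would record what any analyst would do from the present text, and neither the p-value nor the size of the difference would move.

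The ostium rule is the part with possible numerical effect, but it is the kind of derivation that a protocol commonly leaves to the analysis plan or a variable list. It cannot be held against a document that refers to such a list.

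**Conclusion.** No change to the plan is called for. The missing label is a slip of wording: above 15 degrees is meant, and reading it so changes nothing in the planned analysis. The effect of the slip on the two-sided p-value is nil, on the absolute difference nil, and on the sign nil once the text is read in context.

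This rests on two things. First, each patient has one classification before the table is formed. Second, that classification is derived under a rule in the analysis plan or the variable list, which could not be checked. The outcome is secondary, in a pilot of 40 patients without a power calculation, and section 11 already presents its comparisons as hypothesis-generating, so no formal decision depends on it. If the section is reworded for other reasons, naming the favourable band would be a sensible courtesy to readers.

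### Coronary access is compared only as a 15-degree split of an angle the CT already supplies; adding a comparison of the angle would recover much of the information lost with 40 patients

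*Protocol*

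**What the plan says.** Section 8.2 of the protocol names one secondary efficacy outcome, the likelihood of successful coronary access judged on CT after TAVI. Section 3 attaches a directional hypothesis to it: "A strategy of patient-specific rotation will increase the likelihood of successful post-TAVI coronary access assessed by CT".

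Section 11 makes this operational as a proportion of patients, with access feasibility "defined as severe coronary overlap (within 0 degrees to 15 degrees) and less severe coronary overlap (>15 degrees". It does not say whether overlap is counted per coronary artery or per patient.

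In the same section the primary outcome is graded in four bands, from "defined as 0 degrees to 15 degrees being commissural alignment" up to "45.1 to 60.0 degrees being severe commissural misalignment".

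The post-procedural assessment in Section 7.1 collects from the CT the "Coronary ostial relationship with the implanted valve". Section 11 also gives general rules: t-test or Mann-Whitney for continuous variables, and chi-square or Fisher's exact test (when a cell is below 6) for categorical ones. It adds: "A p-value of < 0.05 will be regarded statistically significant, and all hypothesis testing will be two tailed". It states that no power calculation was made and treats the group comparisons as exploratory. Section 13 calls the study a pilot.

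**The concern.** Overlap is an angle, and Section 11 keeps only which side of 15 degrees it falls on. Two arms can differ clearly in how far the valve commissures lie from the ostia and still show similar proportions, because shifts on one side of the cut do not register.

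The cut also sits far from good alignment. For an ostium in the middle of its sinus, severe overlap needs the valve to be rotated into the worst misalignment band. If most valves end up reasonably aligned in both arms, few patients have the event and the comparison says little.

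At stake is what the pilot yields on its second hypothesis. Forty patients will each have an additional CT for research. A result such as 0 of 20 v 4 of 20 could be read as no effect on access when the measured angles would have been more informative.

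**Working it through.** **Inputs from the protocol.** "Target enrollment: 40 patients" (Section 5); overlap cut at 15 degrees, misalignment scale ending at 60 degrees, two-sided 0.05, Fisher's test for small cells (Section 11). The allocation ratio is not given: "Subjects will be randomized to a patient-specific rotational method or a conventional generalized rotational method before the procedure". I assume 20 v 20. The protocol states no event rate, effect size or power, so there is no figure of its own to reproduce.

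**Step 1, geometry.** A misalignment scale ending at 60 degrees implies commissures 120 degrees apart. Let m be the misalignment and e the ostium's offset from mid-sinus.

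- Overlap angle = 60 − |m − e|, with m − e wrapped to ±60 degrees.
- If e = 0, overlap ≤ 15 means 60 − |m| ≤ 15, so |m| ≥ 45. This is the severe misalignment band, apart from the 45.0/45.1 boundary.
- If e varies, the link loosens. At m = 40 with e of SD 10, one given ostium is in severe overlap when e ≤ −5, with probability Φ(−0.5) = 0.31. For either ostium it is 1 − 0.69² = 0.52. At m = 5 both are about 0.

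**Step 2, how often the event occurs.** Simulated, with m normal about 0 and independent left and right offsets; a patient counts if either ostium is within 15 degrees.

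| Misalignment | Aligned (≤15°) | Mid-sinus ostium | Either, scatter 10° | Either, scatter 15° |
|---|---|---|---|---|
| SD 10 | 87% | ~0% | 0.3% | 2.4% |
| SD 15 | 68% | 0.3% | 2.2% | 6.2% |
| SD 20 | 55% | 2.4% | 6.8% | 11.8% |
| SD 25 | 45% | 6.9% | 13.3% | 18.3% |
| SD 30 | 38% | 12.1% | 19.6% | 24.3% |
| Random rotation | 25% | 25% | 34.3% | 37.9% |

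**Step 3, what 20 v 20 can separate with the split.** Two-sided Fisher p against zero events:

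- 0 v 4: 2 × C(20,4)/C(40,4) = 2 × 4,845/91,390 = 0.106
- 0 v 5: 2 × C(20,5)/C(40,5) = 2 × 15,504/658,008 = 0.047

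So if one arm has no events, the other needs at least 5. Power to detect complete elimination is P(Binomial(20, p) ≥ 5): 0.3%, 4%, 17%, 37% and 58% for control rates of 5, 10, 15, 20 and 25%.

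**Step 4, split against angle.** Simulated 20 v 20 trials, smaller of the left and right angles per patient. Fisher's test on ≤15 degrees is set against Mann-Whitney on the angle; entries are the share of trials with p<0.05.

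| Misalignment, fixed-angle v patient-specific arm | Scatter 10°: split v angle | Scatter 15°: split v angle |
|---|---|---|
| SD 25 v SD 12 | 10% v 50% | 16% v 36% |
| SD 20 v SD 10 | 1% v 40% | 5% v 26% |
| SD 30 v SD 15 | 25% v 50% | 24% v 39% |
| Offset 25, SD 20 v offset 0, SD 12 | 53% v 89% | 52% v 77% |
| Random v SD 15 | 73% v 88% | 61% v 78% |
| Random v SD 20 | 48% v 67% | 36% v 54% |

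The angle does better in every row. Part of the gap at low event rates comes from Fisher's test being conservative, but that is the test Section 11 prescribes there.

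**The case against.** Several points on the other side are sound.

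- **The event rate is unknown.** A reader might infer that the secondary outcome sits near its floor. The protocol gives no rate, and Step 2 runs from about 0 to 38%. With SD 25 in the fixed-angle arm, 13 to 18% of patients have the event, or 3 to 4 of 20.
- **The outcome is not severe misalignment under another name.** That identity needs both ostia exactly at mid-sinus. With 10-degree scatter, a valve at 40 degrees of misalignment already puts one or both ostia in severe overlap in 52% of patients, so improving to 5 degrees often does change the category.
- **Low power is acknowledged.** Section 11 disclaims it and Section 13 calls the study a pilot. Section 13's aim of learning how large a difference is refers to commissural alignment; for coronary access it promises only a CT-based analysis of likelihood. It would be wrong to say the split fails the pilot's stated aims.
- **Hypothesis 2 asks about a likelihood**, and the cut is attributed to a cited study. Nothing in the protocol shows that clearance beyond 15 degrees makes access easier, so an angle cannot simply replace the proportion.
- **The angle is not excluded.** Section 11's general rules cover continuous variables, and the variable list and any SAP are not at hand.

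These points rule out replacing the outcome and calling it an error. They do not answer the loss of information: Section 11's item on coronary access names the proportion only, and the advantage of the angle persists when a systematic offset or random rotation makes the event common.

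**Conclusion.** The point holds as a design improvement. Comparing coronary overlap only through a 15-degree split discards much of what 40 post-TAVI CTs can show about the two rotation methods.

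With 10-degree ostial scatter, detection rises from about 10% to 50% for misalignment SD 25 v 12, from about 1% to 40% for SD 20 v 10, and from about 53% to 89% with a 25-degree offset in the fixed-angle arm. With 15-degree scatter the gain is smaller but has the same direction.

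The sizes rest on assumptions the protocol does not supply: 1:1 allocation, evenly spaced commissures, the misalignment distributions, independent normal ostial offsets, and counting the worse coronary per patient. The direction held in all the scenarios tried. The documents do not support a claim that the event is rare, or that the split is wrong as a measure of access feasibility.

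**What to change.** In Sections 8.2 and 11:

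1. Keep the proportion of patients with overlap of 15 degrees or less as the stated measure of access feasibility.
2. Add, as a prespecified secondary analysis, the CT angle in degrees from the coronary ostium to the nearest valve commissure (0 to 60, higher meaning more clearance), taking the smaller of left and right per patient.
3. Compare it between arms with the Mann-Whitney or t-test already named, and report the difference with its 95% CI.

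The cost is protocol wording only, since the angle has to be measured on the same CT to apply the split. There are two drawbacks: one more secondary comparison, and an angle that is less directly readable as access than a proportion, which is why the proportion stays.
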